- 2. Analyze post-operative outcomes including post-operative opioid utilization and pain scores in the first 7 days after surgery. Our working hypothesis is that those patients who receive a single intraoperative methadone dose will have statistically less postoperative opioid utilization and pain scores, without a greater incidence in adverse events (respiratory depression or excessive sedation).

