Pre-operative, Intra-operative, Post-operative Care: Anesthesia and surgical care are not altered for this study except for randomization to the study drug. Oral or IV midazolam for anxiolysis may be given at standard dosing. Anesthetic induction via inhaled sevoflurane or intravenous agents are to be given at the anesthesiologist's discretion.

Patients in the short-duration opioid group receive short-duration opioids (IV fentanyl and/or hydromorphone), given as needed throughout the intraoperative period, per usual practice at practitioner's discretion. Patients in the long-duration opioid group receive IV methadone HCl at 0.1mg/kg. These subjects receive methadone as their only intraoperative opioid, given as a single bolus at anesthetic induction. If needed, a second cohort will receive or 0.15mg/kg of age-based ideal body weight. Following extubation, patients may receive incremental doses of

0.1mg/kg up to a maximum of 0.5mg/kg of dexmedetomidine (dosed at age-based ideal body weight) for sedation if needed, contingent upon adequate ventilatory rate.

For analgesia in the Post-Anesthesia Care Unit (PACU), patients in both groups may receive typical short-duration opioids (fentanyl or hydromorphone) as per usual routine care. It is not necessary that patients receive the same opioid postoperatively as intraoperatively. Post-op opioids orders are written by the pediatric anesthesiologist and opioids are given by PACU nurses per standard practice, based on developmentally appropriate pain scales (FLACC, Wong-Baker Faces, VAS) and institutional practice.

Pain scores via developmentally appropriate and validated pediatric pain scales will be confirmed by a blinded research coordinator OR a blinded secondary pediatric PACU nurse and charted in the EMR prior to administration of opioid analgesics. Adverse events will be recorded by a research coordinator who is blinded to randomization allocation and include: Respiratory depression (respiratory rate <10/min), reintubation, decreased oxygen saturation <85% for 30 seconds, excessive sedation (Pasero Opioid-induced Sedation Scale (POSS) score 3>1 hour, 4>15 minutes), unexpected PICU admission, and vomiting in PACU.

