### **Data Analysis & Statistical Considerations**

Descriptive statistics for each treatment group will be computed for patient demographic and characteristic variables. Since our randomization scheme will have balanced the age effect between treatment groups, we anticipate the demographic and patient characteristic variables will be balanced across groups. For the continuous outcome measures (primary and most of secondary outcomes), we will conduct two-sample t-test to test the outcome difference (e.g., total OME difference) between treatment groups. For categorical outcomes (e.g., PACU side effects and adverse events), chi-square or Fisher exact tests will be applied as appropriate. Considering this is a pilot study for dose finding, we will relax the significance threshold to 0.1 for the interim analysis. Using the primary outcome, total OME/kg as an example, a two-sample t-test will be performed for comparing total OME difference between 20 methadone (0.1mg/kg) treated patients to 10 controls based on significance threshold of 0.10. If methadone showed significant effect on the outcome measure, the higher dose arm (0.15 mg/kg age ideal body weight) will be pursued. In the final analysis, similarly, two-sample test

will be used to test the total OME difference between methadone and control groups for both dose levels. To correct for multiple testing, the significance threshold in the final analysis will be set at 0.025. If there are covariates showing significant difference between treatment groups, we will perform multivariable linear regression analysis to test the treatment effect after adjusting for one selected covariate and examine if the treatment effect remains the same as that found in the two-sample t-test. The reason to restrict to one covariate in the model was to avoid model overfitting considering there will be only 20 samples per group. Similar analysis strategy will be applied to other outcome measures.

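### Pain scores charted on three age-dependent scales appear headed for one unstratified t-test, which costs precision and ignores the age bands used in randomisation (minor)

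*Combined protocol and SAP*

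**What the plan says.** All references are to the combined protocol and SAP.

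- **Purpose of the Study, Aim 2.** The aim is to "Analyze post-operative outcomes including post-operative opioid utilization and pain scores in the first 7 days after surgery". Its hypothesis is that methadone patients "will have statistically less postoperative opioid utilization and pain scores", so pain is compared between arms.
- **Design & Procedures, paragraphs on PACU care.** Three instruments are named where the text explains how PACU opioids are given: "based on developmentally appropriate pain scales (FLACC, Wong-Baker Faces, VAS) and institutional practice". The next paragraph covers the recorded scores: "Pain scores via developmentally appropriate and validated pediatric pain scales will be confirmed by a blinded research coordinator OR a blinded secondary pediatric PACU nurse". It gives no age cut-offs and no common range, and does not ask for the instrument to be recorded with the score.
- **Study Interventions.** Randomisation is blocked within ages 3-6, 7-12 and 13-17, because pain tolerance may differ by age.
- **Data Analysis & Statistical Considerations.** "For the continuous outcome measures (primary and most of secondary outcomes), we will conduct two-sample t-test to test the outcome difference". For the rest, "Similar analysis strategy will be applied to other outcome measures". Covariate adjustment is conditional: "If there are covariates showing significant difference between treatment groups, we will perform multivariable linear regression analysis", with one covariate at most.
- **Subject Recruitment and Compensation.** Daily surveys run on days 1-7. No pain instrument is named for the home period.

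**The concern.** The sample runs from age 3 to under 18, so more than one instrument will be in use. Nothing says that a point on one scale equals a point on another. If the scales sit at different average levels, a pooled t-test counts that difference as error variance.

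The randomisation is built around age, which should largely determine the scale, but the planned test does not use the age bands. The conditional regression is unlikely to fill the gap: it needs a significant imbalance between arms, which age blocking makes improbable, and it never names instrument or age band.

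At stake is the Aim 2 pain comparison, and the usefulness of this pilot's pain means and SDs for planning a later trial. If the instrument is not stored with each score, an analysis by instrument may be impossible afterwards.

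**Working it through.** **The plan's own power.** The only power stated is for total OME. A two-sided equal-variance t-test (noncentral t) gives:

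- Interim, 20 vs 10, difference 0.3, SD 0.3, alpha 0.10: 80.9% (plan: 80%).
- Final, 20 vs 20, difference 0.31, SD 0.3, alpha 0.025: 82.0% (plan: 82%).

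Both reproduce. Neither concerns pain, for which the plan gives no SD, difference or power.

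**Inputs for pain.** From the plan: 20 vs 20 and alpha 0.025 (taken as two-sided). Assumed: within-instrument SD 2 on 0-10, true difference 2, about one third of children on each instrument, the same split in both arms, and instrument means at 0, g/2 and g, where g is the gap between highest and lowest.

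**Variance added by pooling.** Three equally frequent, equally spaced means have variance g²/6, so the pooled SD is √(4 + g²/6):

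- g = 0: √4.000 = 2.00
- g = 1: √4.167 = 2.04
- g = 2: √4.667 = 2.16
- g = 3: √5.500 = 2.35

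**Effect when instruments are balanced.** The difference in means is unaffected by the instrument levels, so its true standard error stays at 2 × √(2/20) = 0.632 and the signal is 2/0.632 = 3.16 standard errors. The t-test, however, uses the pooled SD. Its critical value (2.334 on 38 df) is in effect multiplied by pooled SD/2. Approximate power is Φ(3.16 − 2.334 × SD/2):

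- g = 0: Φ(3.16 − 2.33) = Φ(0.83), about 80%
- g = 1: Φ(3.16 − 2.38) = Φ(0.78), about 78%
- g = 2: Φ(3.16 − 2.52) = Φ(0.64), about 74%
- g = 3: Φ(3.16 − 2.74) = Φ(0.42), about 66%

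Simulation under the same inputs gives about 79%, 78%, 73% and 66-67%. The last figure shifts by a point or so with how 20 children divide into thirds. Type I error falls from 2.5% at g = 0 to 0.9% at g = 3.

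**Stratified analysis.** With stratum as a factor, the error SD returns to 2 on 36 df (critical value 2.339). Power is 79% at every gap and type I error is 2.5%. This assumes that instrument follows the stratum; to the extent that it does not, recovery is partial.

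**Without balance.** If instrument fell purely at random, power is that of a t-test with the pooled SD: 79%, 77%, 72% and 64%. Type I error stays at 2.4-2.5%.

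**Other assumptions.** With SD 2.5, a difference of 1.033 SD and an 8/8/4 split per arm, pooled power is 82% with equivalent scales, 80% with offsets of −1/0/+1 and 70% with −2/0/+2. Stratified power is about 81-82% throughout.

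**The case against.** The strongest reply is that the plan never says pain scores will be pooled. The analysis section does not name pain, limits the t-test to most of the secondary outcomes, and no pain summary is defined. That is right, and pooling is an inference here. But the t-test is the only method offered for continuous outcomes, and no analysis by scale, rescaling or stratification appears.

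The second reply is that age blocking already deals with instrument. It does so in large part: it should roughly balance instruments between arms. It does not remove between-instrument variance from a test that ignores the bands.

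Four stronger readings are tempting and are not supported:

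- *Institutional practice picks the scale, so scales vary within an age or within a child.* In "based on developmentally appropriate pain scales (FLACC, Wong-Baker Faces, VAS) and institutional practice", institutional practice is a second basis for giving opioids. The documents name only developmental appropriateness as the basis for the scale, and are silent on variation within an age or a child.
- *Chance imbalance in instrument will produce false positives.* The calculation shows type I error at or below 2.5%, with or without balance.
- *A VAS on 0-100 mixed with 0-10 scores would wreck the comparison.* It would, but no range is stated for any scale and nothing points to unconverted entry.
- *Observer scores read low in sedated children and favour one arm.* The documents say neither that, nor that one arm is more sedating. Excessive sedation is recorded separately as an adverse event.

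**Conclusion.** The point holds as a minor one. The plan collects pain on several instruments, compares it between arms, and offers only an unstratified test with no common range. If scores are pooled, the loss under the assumed inputs is about 1 point of power for a 1-point gap between instruments, 6 for 2 points and 12-13 for 3 points, with a test that becomes conservative and an estimate that is hard to interpret.

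These sizes rest on assumed SD, difference, instrument mix and gaps. The documents also do not say who rates each scale; treating FLACC as observer-rated and the other two as self-reported is an assumption from the nature of the instruments.

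A reader might infer a biased pain comparison or a threat to the main result. The documents support neither. Randomisation is blocked by age, the primary outcome is total OME/kg, and the escalation rule uses PACU opioid use and adverse events. Pain scores help to guide PACU opioid administration, but they are not an endpoint in either.

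**What to change.** **Data collection (Design & Procedures).** Record the instrument and the rater with each pain score, and store every score on 0-10. Leave the bedside choice of scale as it is, because the same scores guide PACU opioid administration and the protocol says that care is otherwise unaltered.

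**Analysis (Data Analysis & Statistical Considerations).** Name pain score explicitly. Replace the plain t-test for pain with a comparison that has randomisation age band (3-6, 7-12, 13-17) as a stratum, whether or not the bands look imbalanced. As a sensitivity analysis, show results by instrument, with observer-rated and self-reported scores apart.

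**Days 1-7.** Name the instrument used in the home surveys, and apply the same recording, range and stratified analysis.

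**Cost.** Instrument and rater recorded with each score, a few sentences of text, and two degrees of freedom (38 to 36). If the scales turn out to be equivalent, power stays at about 79% under the inputs above. No extra patients or visits are needed.

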#### **Design & Procedures**

Study Design: Single center, randomized, double blind, parallel-group dose escalation investigation. All patients will receive standard monitoring for anesthesia and postoperative care. Surgical and anesthesia care (except for intraoperative opioid management) are not altered for study purposes. Subjects are randomized 2:1 to either long-duration (methadone) or short-duration opioid (fentanyl, hydromorphone). The use of any short acting opioid (ie: fentanyl, hydromorphone or both) is considered the control group and total dose, timing of administration, frequency of administration, and dose per administration of either/both short acting opioids will be administered at the discretion of the anesthesiologist as per standard of care practice. Because methadone analgesia for pediatric tonsillectomy has not previously been studied, this pilot study will use escalating dose groups to determine the optimal dose for this procedure. In order to achieve this, our trial design will include two periods. In the first period, we will randomly assign 20 patients to methadone 0.1 mg/kg and 10 patients to typical shortduration opioid (controls). An interim analysis will be conducted to determine if we should escalate to the higher dose of methadone. Methadone dose escalation to 0.15mg/kg age ideal body weight will occur if there is no difference in non-methadone PACU opioid use and no increased adverse events. If proceeding to the second period, we will recruit 20 patients for 0.15 mg/kg methadone and 10 patients as controls. Sample size for this pilot investigation was based on prior studies.

Defining an optimal dose of methadone is a crucial aim of this study, which will allow for future investigations, but is not a primary or secondary outcome. The dose finding nature of this study requires interim assessments after each methadone dose cohort. After the first 20 methadone subjects at 0.1mg/kg age ideal body weight, there will be a planned partial analysis of PACU opioid use. Methadone dose escalation to 0.15mg/kg age ideal body weight will occur if there is no difference in non-methadone PACU opioid use and no increased adverse events. Sample size for this pilot investigation was based on prior studies.

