### Selection of Subjects

Patient Selection: Patients undergoing tonsillectomy +/- adenoidectomy at Duke University Hospital and Duke Regional Hospital or a Duke Affiliated Ambulatory Surgical Center (including Davis Ambulatory Surgical Center) will be recruited for enrollment. Selection criteria are as follows:

Inclusion Criteria (IC): Children age >=3 and <18 yrs having elective tonsillectomy +/-adenoidectomy with signed, informed consent by parent or legal guardian. Post pubescent females are required to have a negative pregnancy test within 48 hours of surgery. Children >12 years must give assent.

Exclusion Criteria (EC): Patients with any of the following: 1. history of or known liver or kidney disease 2. Consistent daily opioid use for chronic pain (defined as ongoing pain >3 months) 3. severe sleep apnea (Sleep study with Apnea Hypopnea Index (AHI) > 10). 4. planned admission to the Pediatric Intensive Care Unit (PICU) following surgery 5. additional procedures under the same general anesthetic for which outpatient opioids would be prescribed.

Patients undergoing procedures such as PE tubes, nasal endoscopy, Auditory Brain Response tests, imaging studies do not have to be excluded.

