#### **Study Interventions**

Study Intervention and Randomization: Subjects in each cohort will be randomized 2:1 methadone to short acting opioid using randomization tables generated by The Biostatistics Group within the Department of Anesthesia. Each subject is assigned the next number. To consider children in different age may have different pain tolerance, we will balance the treatment groups by age. That is, we will generate a set of blocked randomization numbers for three age groups, 3-6, 7-12, and 13-17 years old. Anesthesia providers receive a sealed envelope or email with Group (drug) assignment, group-specific instructions, and are advised on study procedures. To ensure full double-blinding, subjects, investigators, and study team members evaluating patients will be blinded to drug treatment. The rationale for 2:1 randomization is to achieve the same sample size for each group since we anticipate 2 methadone cohorts, thus final groups (methadone 0.1 mg/kg, methadone 0.15 mg/kg, controls) would each have 20 subjects.

As clarified above, the use of a short duration opioid in this specific study population (tonsillectomy 3-18 year olds) is a standard of care procedure. Methadone is standard of care in pediatric cardiac surgery, pediatric spine surgery and precuts excavatum surgery (3-18 year olds). Not counting the randomization, the dosing and administration of all 3 of these drugs (methadone, fentanyl, hydromorphone) are in line with standard of care practices for pediatric population of between 3 and less than 18 years and are routinely used both in and out of the operating room environment.

Regarding the clinical study of an investigational drug that would be IND exempt, the following ARE true for this study (see below):

- The investigation of a drug that is lawfully marketed in the US and the following 5 criteria are met:

the study is not designed to support approval of a new indication or change in labelling: No new indications sought

the study does not intend to support significant change in advertising of the product: No new advertising sought

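### Respiratory rate is compared between arms only as an event below 10/min at all ages, so the planned test has little power to show that methadone slows breathing

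*Combined protocol and SAP*

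**What the plan says.** The adverse events in Design & Procedures start with "Respiratory depression (respiratory rate <10/min), reintubation, decreased oxygen saturation <85% for 30 seconds" and continue with "excessive sedation (Pasero Opioid-induced Sedation Scale (POSS) score 3>1 hour, 4>15 minutes), unexpected PICU admission, and vomiting in PACU". All are recorded as having occurred or not.

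Eligibility (Selection of Subjects) is "Children age >=3 and <18 yrs having elective tonsillectomy", and the 10/min cut-off is the same throughout that range. Age enters the design through randomization: "we will generate a set of blocked randomization numbers for three age groups, 3-6, 7-12, and 13-17 years old" (Study Interventions). The reason given there is pain tolerance.

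The safety part of the Aim 2 hypothesis (Purpose of the Study) is that methadone patients do better "without a greater incidence in adverse events (respiratory depression or excessive sedation"). The test is stated in Data Analysis & Statistical Considerations: "For categorical outcomes (e.g., PACU side effects and adverse events), chi-square or Fisher exact tests will be applied as appropriate". No section describes an analysis of respiratory rate as a number or by age.

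**The concern.** To apply a cut-off of 10/min someone must read the rate, so a number exists for each child. The plan keeps only which side of the cut-off it fell on. A child whose usual rate is well above 10/min can slow appreciably and still count as no event.

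Respiratory depression is one of the two harms named in Aim 2, and the protocol says methadone has not been studied for this operation. In groups of 10 and 20 children, a non-significant comparison of a few events could be taken as evidence that methadone does not slow breathing, when the test could hardly have shown it.

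**Working it through.** **1. The plan's own power figures.** The power calculation uses a two-sample t-test with equal variances for total OME. Power comes from the noncentral t with df = n1 + n2 − 2 and noncentrality d/√(1/n1 + 1/n2). Sidedness is not stated; two-sided reproduces the figures.

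- Interim: "we will randomly assign 20 patients to methadone 0.1 mg/kg and 10 patients to typical shortduration opioid (controls"), d = 0.3/0.3 = 1, alpha 0.10 ("we will relax the significance threshold to 0.1 for the interim analysis"). Power 80.9%; the plan says 80%.
- Final: 20 vs 20, d = 0.31/0.3 = 1.033, alpha 0.025. Power 82.0%; the plan says 82%.

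No power is stated for any safety outcome.

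**2. Assumed inputs.** The documents give no mean, SD or event rate for respiratory rate. Assumptions: the lowest PACU rate is normal with mean m in controls (14, 16, 18, 20/min), mean m − 3 under methadone, and common SD s (3, 4, 5). The alphas of step 1 are carried over. The plan illustrates them with OME and says that a similar strategy applies to other outcomes.

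**3. Event rates and power.** Control incidence = Φ((10 − m)/s); methadone incidence = Φ((13 − m)/s). For example, m = 16 and s = 3 give Φ(−2) = 2.3% and Φ(−1) = 15.9%. Fisher power is the sum of the binomial probabilities of all tables with two-sided p ≤ alpha. Continuous power uses the formula of step 1 with d = 3/s.

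| SD | Control mean | Incidence, control vs methadone | Fisher, interim | Fisher, final | Continuous, interim / final |
|---|---|---|---|---|---|
| 3 | 14 | 9.1% vs 36.9% | 38% | 32% | 81% / 79% |
| 3 | 16 | 2.3% vs 15.9% | 7% | 6% | 81% / 79% |
| 3 | 18 | 0.4% vs 4.8% | 0.03% | 0.02% | 81% / 79% |
| 3 | 20 | 0.04% vs 1.0% | 0% | 0% | 81% / 79% |
| 4 | 14 | 15.9% vs 40.1% | 26% | 20% | 60% / 52% |
| 4 | 16 | 6.7% vs 22.7% | 15% | 10% | 60% / 52% |
| 4 | 18 | 2.3% vs 10.6% | 1% | 1% | 60% / 52% |
| 4 | 20 | 0.6% vs 4.0% | 0.01% | 0.01% | 60% / 52% |
| 5 | 14 | 21.2% vs 42.1% | 19% | 13% | 45% / 34% |
| 5 | 16 | 11.5% vs 27.4% | 15% | 9% | 45% / 34% |
| 5 | 18 | 5.5% vs 15.9% | 5% | 3% | 45% / 34% |
| 5 | 20 | 2.3% vs 8.1% | 0.4% | 0.3% | 45% / 34% |

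The uncorrected chi-square test does better but stays below the continuous analysis in every row. Its highest values, at m = 14 and s = 3, are 55% (interim) and 45% (final).

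**4. Why the power is so low.** With no control events, Fisher needs at least 6 of 20 methadone children below 10/min. At 20 vs 10, 5 events give p = 0.14 and 6 give p = 0.074. At 20 vs 20, 5 give p = 0.047, above 0.025, and 6 give p = 0.020.

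**5. The escalation condition.** Design & Procedures makes escalation depend on there being no increase in adverse events. Protections against Risk, item iii, allows it only if the initial dosing group has none at all. Under the second wording, the chance that at least one of 20 methadone children falls below 10/min is 1 − (1 − p)^20. With s = 3 and control means 14, 16, 18 and 20, this is >99.9%, 97%, 62% and 18% with the slowing, and 85%, 37%, 7% and 1% without it.

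**The case against.** **Respiratory safety has more than one measure.** A reader might infer that it rests on one cut-off. It does not: the same list has reintubation, desaturation, sedation by POSS and unexpected PICU admission. This stands, and the point is confined to respiratory rate. The other items are also yes/no events, and none measures slowing itself.

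**Escalation.** A reader might infer that slower breathing would pass unnoticed into the higher dose. The documents do not support that. No section ties the adverse-event condition to a Fisher test at 0.10, and step 5 shows that the zero-event wording would often block escalation. That wording involves no control group, however, so it does not serve the between-arm claim of Aim 2.

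**Aim 2 is about incidence.** Comparing counts answers the question as written. Where Fisher power is near zero, few children meet the protocol's definition of harm: about 1% of methadone children with control mean 20 and SD 3. This stands, and it is why the continuous analysis should be supportive and should not replace the counts.

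**The inputs are assumed.** Power close to that for the primary outcome appears only because a 3/min shift with SD 3 is d = 1, the plan's own OME effect size. With SD 4 or 5 it falls well short. The model also gives all ages one mean. This stands as to size. The continuous analysis remains ahead in every row.

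**Charting.** The documents describe standard or routine monitoring and do not say how often PACU respiratory rate is charted. A lowest value depends on the number of readings and length of stay. This stands, and the fix allows for it.

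**Conclusion.** The point holds for respiratory rate and for the between-arm comparison. With a 3/min slowing, the planned Fisher test would show it in 0-38% of trials at the interim and 0-32% at the final analysis, over control means of 14 to 20/min and SDs of 3 to 5. A continuous comparison would show it in 45-81% and 34-79%. These ranges rest on assumed means and SDs, normality, two-sided tests and the plan's alphas applied to safety.

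The event definitions and the choice of a test for counts are not errors; this is an inexpensive gain in sensitivity. Separately, the two wordings of the adverse-event condition for escalation contradict each other and must be reconciled.

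**What to change.** Optional. Keep every event definition as it is. In Data Analysis & Statistical Considerations, add a supportive between-arm comparison of:

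- each child's lowest charted PACU respiratory rate and lowest saturation, as continuous measures;
- each child's highest POSS, as an ordinal measure.

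Adjust for the three randomization age bands, use a fixed PACU window common to both arms, and report each difference with a confidence interval at the interim and final analyses.

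Reconcile Design & Procedures with Protections against Risk, item iii, on the adverse-event condition. That choice belongs to the investigators.

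The cost is a paragraph of statistical text and three summary values per child. The downside is that a statistically clear difference may be clinically small, so it must be read beside the events.

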#### Protections against Risk:

- i) Eligibility criteria exclude patients with known renal or hepatic disease, which may affect opioid disposition, pregnant females, those with severe sleep apnea with apnea hypopnea index > 10 and those who require planned ICU admission post operatively.
- ii) Methadone dosing is fixed, using age based ideal body weight, rather than actual body weight, to obviate risk of excessive dosing due to obesity.
- iii) Dose escalation will only occur if there are no adverse events in the initial dosing group

- iv) If nausea and/or vomiting occur, patients will be treated using the standard of care for all post-anesthesia nausea and vomiting. Respiratory depression with a respiratory rate <10 breaths/minute or hypoxia with oxygen saturation less than 85% for > 30 seconds will be monitored closely. If treatment is required, naloxone will be used. Patients will be routinely monitored by pulse oximetry, and receive supplemental oxygen if dictated, according to standard anesthesia practice.
- v) Research subjects will receive pre-operative, intra-operative and post-operative routine monitoring by anesthesiology and nursing staff.
- vi) The risk of breach of protected health information will be minimized by limiting the number of people within the research group who have access to identified data which will be described in the data monitoring safety plan.

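### Sedation or brief desaturation reversed before its time limit, with respiratory rate at 10 or above, is not a listed adverse event, and naloxone use is not listed either

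*Combined protocol and SAP*

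**What the plan says.** The only operational list of adverse events is in Design & Procedures, under pre-, intra- and post-operative care. It opens with "Adverse events will be recorded by a research coordinator who is blinded to randomization allocation and include" and then names these items:

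- "Respiratory depression (respiratory rate <10/min), reintubation", with no minimum duration;
- "decreased oxygen saturation <85% for 30 seconds", so that a shorter dip is not listed;
- "excessive sedation (Pasero Opioid-induced Sedation Scale (POSS) score 3>1 hour, 4>15 minutes), unexpected PICU admission, and vomiting in PACU".

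Naloxone appears only under Protections against Risk, item iv, and only as a treatment. That item says "Respiratory depression with a respiratory rate <10 breaths/minute or hypoxia with oxygen saturation less than 85% for > 30 seconds will be monitored closely" and continues "If treatment is required, naloxone will be used". It also provides for supplemental oxygen under standard practice. No text says how an episode that treatment ends before its time limit is to be scored.

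Adverse events then serve two purposes. In Design & Procedures, escalation to the second dose depends on "no difference in non-methadone PACU opioid use and no increased adverse events". Protections against Risk, item iii, sets a different condition: the first dose group must have had none at all. Aim 2 in Purpose of the Study expects lower pain and opioid use without more adverse events, and names respiratory depression and excessive sedation as the events of interest.

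**The concern.** A duration requirement works as an outcome definition when the state runs its natural course. Here staff are expected to intervene, and intervention can stop the clock. For sedation, and to a small extent for desaturation, whether a child has an event then depends partly on how quickly someone acted as well as on how deeply the child was sedated. A child who needed reversal can be recorded as event-free.

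The protocol states that methadone has not previously been studied in pediatric tonsillectomy, so this small set of events is its main safety evidence. The same events decide whether a higher dose is opened. Excessive sedation is one of the two events that Aim 2 names, and it is where the gap is widest.

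**Working it through.** **1. Apply the listed criteria to single cases.** Each child is assumed to have no vomiting, reintubation or unexpected PICU admission.

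| Course | Listed event? |
|---|---|
| POSS 4 for 16 minutes, untreated, rate 10 or above | Yes |
| POSS 4, reversed at 5 minutes, rate 11 | No |
| POSS 3, reversed at 45 minutes, rate 10 or above | No |
| Saturation 84%, corrected at 20 seconds, rate 10 or above | No |
| Respiratory rate 9, reversed at once | Yes |

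The gap therefore has two conditions: treatment comes before the time limit, and the respiratory rate stays at 10 or above. The window is up to 1 hour (POSS 3) or 15 minutes (POSS 4) for sedation, but only 30 seconds for desaturation. Sedation is the substantive part.

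**2. The plan's own figures.** The power figures concern total OME, not adverse events. They reproduce with a two-sided equal-variance t-test (noncentral t):

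- Interim: noncentrality 0.3 / (0.3 × √(1/20 + 1/10)) = 2.58, 28 df, alpha 0.10. Power is 80.9%, against 80% stated.
- Final: noncentrality 0.31 / (0.3 × √(1/20 + 1/20)) = 3.27, 38 df, alpha 0.025. Power is 82.0%, against 82% stated.

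No adverse-event rate or power is given, so the rates below are assumptions.

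**3. The none-at-all condition (Protections against Risk, item iii).** With true event probability p per methadone child and a share m missed, the chance that none of 20 has a recorded event is (1 − p(1 − m))^20.

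| Assumed p | None missed | Half missed |
|---|---|---|
| 5% | 0.95^20 = 36% | 0.975^20 = 60% |
| 10% | 0.90^20 = 12% | 0.95^20 = 36% |
| 20% | 0.80^20 = 1% | 0.90^20 = 12% |
| 30% | 0.70^20 = 0.1% | 0.85^20 = 4% |

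This treats every event as one that could be missed. Vomiting and low respiratory rate cannot be missed in this way. Suppose 10% of children independently have an event of the always-counted kind and 5% have one that could be missed. The chance of a clean record is then 0.90^20 × 0.95^20 = 4% with nothing missed, and 0.90^20 × 0.975^20 = 7% with half missed.

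**4. The comparative condition (Design & Procedures).** Assume it is judged by a two-sided Fisher test at 0.10 on 20 versus 10 children, with the methadone rate higher. The exact chance of flagging an excess is:

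- true rates 30% versus 10%: 22% with full recording, 4% if half are missed in both arms;
- true rates 20% versus 5%: 12% with full recording, 1% if half are missed in both arms.

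As a single example, take 3/20 versus 0/10. The hypergeometric weights out of C(30,3) = 4060 are 1140 for this table, and 900 and 120 for the two less likely ones. So p = 2160/4060 = 0.53, even when all three events are counted.

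**The case against.** Much of the other side's case stands.

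- A reader might infer that any promptly treated event is lost. The list does not support that: respiratory rate below 10/min, reintubation, unexpected PICU admission and vomiting count at any duration.
- A reader might infer that the events needing naloxone are the ones dropped. Item iv places naloxone directly after low respiratory rate and desaturation beyond 30 seconds. Both are already listed, so naloxone given for them is captured through its trigger. The documents describe no use of naloxone for sedation alone.
- A reader might infer a tilt towards methadone looking safe. Anesthesia providers do receive the assignment and could act earlier after methadone, but this is conjecture. Control opioids are discretionary, the protocol calls the anesthetic risks of the two groups similar, and it gives no timing of treatment.
- A reader might add that one respiratory-rate cut-off across ages 3 to 17 misses these children. No figure in the documents bears on that.
- The comparison is weak at 20 versus 10 whatever is recorded, and under item iii a single vomiting episode already blocks escalation. At an assumed vomiting rate of 10% or 15%, the chance of none in 20 is 12% or 4%.

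One defence does not remove the point. The list is introduced as inclusive, so other events could be recorded, but nothing requires anyone to record naloxone or a shortened episode. A count that decides escalation should not rest on discretion. Duration limits may also sensibly screen out ordinary emergence from anesthesia, and the fix keeps them for untreated episodes.

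**Conclusion.** The point holds in a limited form. Sedation, and marginally desaturation, that is treated before its time limit while respiratory rate stays at 10 or above is not a listed event, and giving naloxone is not one either. This can understate sedation in the escalation data and in the Aim 2 comparison.

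Neither the size nor the direction between arms can be established, because the documents give no event rates and no share treated early. The consequence is clearest under the none-at-all condition, where one unrecorded event can change the decision. The shift from 36% to 60% assumes a 5% true rate, half missed, and no other event in the group. It shrinks to 4% versus 7% if always-counted events occur in 10% of children. Under the comparative condition, sample size is the larger limitation. The two conditions also conflict, so the effect of a missed event is not fully defined until they are reconciled.

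**What to change.** In the adverse-event paragraph of Design & Procedures:

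- add any naloxone administration to the recorded adverse events;
- state that a sedation or desaturation episode ended by treatment before its time limit meets the outcome definition;
- record each child's worst POSS, and the start and end of each such episode.

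These are changes to recording and scoring only; treatment thresholds stay as they are. A broader trigger that counts any supplemental oxygen or airway support is not recommended. It would be subjective, item iv treats oxygen as routine practice, and it would reset the escalation criterion.

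Separately, the sponsor should reconcile the comparative condition in Design & Procedures with the none-at-all condition in Protections against Risk, item iii, and state which recorded events feed the decision.

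The cost is a wording change, a few more data fields and slightly more events counted. The protocol mentions charting in the EMR only for pain scores, so it should not be assumed that the added fields are already captured.
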